#### **9.3.1.1. Adverse Drug Reaction**

An adverse drug reaction (ADR) is defined as a noxious and unintended response to a medication related to any doses where there is at least a reasonable possibility, or the relationship cannot be ruled out, that it is related to CAB PrEP.

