### 9.1. Specific Adverse Events to be Documented in this Study

Please refer to the USPIs for CAB tablets for PrEP and APRETUDE for additional safety information [[APRETUDE](#), 2021].

Adverse events that occur during the trial should be evaluated by the PrEP provider and graded according to the Division of AIDS (DAIDS) toxicity scales Version 2.1 July 2017.

AEs and SAEs that are required to be recorded as defined in the eCRF include:

- AEs/ADRs considered related to CAB PrEP
  - Note: Non-serious injection site reactions do not have to be reported to the CRO..
- AEs/Adverse drug reactions (ADRs) reported at the Baseline/Month 1 visit that are considered related to CAB tablets for PrEP (if used as optional oral lead-in)
- All AEs, including ISRs, whether considered related or not, that cause the participant to discontinue CAB PrEP

- All SAEs whether related to CAB PrEP or not

The PrEP provider are obliged to collect and report from the time of informed consent to PSP's completion of study or study withdrawal, all non-serious ADRs, (excluding non-serious ISRs), AEs leading to withdrawal and all SAEs listed above, to the CRO.

As ISRs have been well characterized throughout the clinical development program for CAB PrEP and are considered common adverse drug reactions for CAB PrEP, therefore only serious ISRs and ISRs leading to discontinuation are required to be reported as described in above.

Non serious AEs that are considered not related to CAB PrEP by the SSP or do not lead to withdrawal, should be documented in the source documents but will not be documented in the eCRF, as this information has been extensively collected in PrEP clinical trials, no further information is needed to characterize these events.

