### **9.3.1. Definition of adverse events**

An AE is any untoward medical occurrence in a PSP, temporally associated with the use of CAB PrEP, whether or not considered related to a medicinal product.

NOTE: An AE can therefore be any unfavorable and unintended sign (including an abnormal laboratory finding), symptom, or disease (new or exacerbated) temporally associated with the use of CAB PrEP.

AEs will be reported by the PSP (or, when appropriate, by a caregiver, surrogate, or the participant's legally authorized representative [LAR]) and be collected and stored in the participants source documentation.

The PrEP provider should assess all reported AEs and SAEs for follow-up medical management and to determine relatedness to CAB PrEP. When a causality relationship is

determined by the PrEP provider to be related to CAB PrEP, this must be recorded as a treatment related AE or SAE.

Adverse events that occur during the trial should be evaluated by the SSP and graded according to the Division of AIDS (DAIDS) toxicity scales Version 2.1 July 2017. Further details of the definitions of adverse events (AE) or serious adverse events (SAEs) can be found in [ANNEX 4](#).

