
Assessment of Causality
 
 
The PrEP Provider is obligated to assess the relationship between study intervention and each occurrence of each AE/SAE. The PrEP Provider will use clinical judgment to determine the relationship.
 
A reasonable possibility of a relationship conveys that there are facts, evidence, and/or arguments to suggest a causal relationship, rather than a relationship cannot be ruled out.
 
Alternative causes, such as underlying disease(s), concomitant therapy, and other risk factors, as well as the temporal relationship of the event to study intervention administration will be considered and investigated.
 
The PrEP Provider will also consult the Investigator's Brochure (IB) and/or Product Information, for marketed products, in his/her assessment.
 
For each AE/SAE, the PrEP Provider must document in the medical notes that he/she has reviewed the AE/SAE and has provided an assessment of causality.
 
There may be situations in which an SAE has occurred and the PrEP Provider has minimal information to include in the initial report to the Sponsor. However, it is very important that the PrEP Provider always make an assessment of
 

--

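### Sections 9.1, 9.3.1.1 and Annex 4 give incompatible rules for which non-serious adverse events enter the eCRF

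*Protocol*

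**What the plan says.** Section 9.1 of the protocol limits eCRF recording to certain events. Its list includes "AEs/ADRs considered related to CAB PrEP" and "All AEs, including ISRs, whether considered related or not, that cause the participant to discontinue CAB PrEP", together with all serious AEs. Non-serious injection site reactions (ISRs) are reported only if they lead to discontinuation. The opening of Section 9 and the AE review rows of both schedules (Annexes 1 and 2) give the same rule: drug-related AEs, and AEs that lead to discontinuation.

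Three other statements bear on how that rule works.

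- **Threshold in Section 9.3.1.1.** An adverse drug reaction (ADR) is a response "where there is at least a reasonable possibility, or the relationship cannot be ruled out, that it is related to CAB PrEP".
- **Threshold in Annex 4 (Section 11.4.4, causality).** A reasonable possibility "conveys that there are facts, evidence, and/or arguments to suggest a causal relationship, rather than a relationship cannot be ruled out".
- **Exclusion sentence in Section 9.1.** "Non serious AEs that are considered not related to CAB PrEP by the SSP or do not lead to withdrawal" go into the source documents "but will not be documented in the eCRF".

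On who judges, Section 9.3.1 and Annex 4 assign causality to the PrEP provider. The exclusion sentence names the SSP instead. For grading, Section 9.1 names the PrEP provider, while Section 9.3.1 says: "Adverse events that occur during the trial should be evaluated by the SSP and graded".

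**The concern.** In a protocol that records every AE, causality is an attribute that can be re-examined in the analysis. Here, for part of the non-serious AEs, it is the entry condition for the database. If sites work from different definitions of relatedness, the eCRF will hold different sets of events and nothing in it will show which definition was used. The analysis cannot correct for this, because the rule acts at collection. The exclusion sentence adds a second problem: a site that applies it literally would omit events that the list directly above it requires.

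**Working it through.** No arithmetic applies, because the protocol gives no expected AE or ADR rate. The check sets the rules side by side.

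**1. Threshold.** Sort events by the strength of the link to CAB PrEP.

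| Event | ADR under 9.3.1.1 | Reasonable possibility under Annex 4 |
|---|---|---|
| Positive grounds for a link | yes | yes |
| No positive grounds, but link cannot be excluded | yes | no |
| Link excluded | no | no |

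The two agree on the first and third rows and differ only on the middle one. Both are operative. Section 9 sends sites to Annex 4 for assessing causality, while Sections 9.1 and 9.1.1 require collection of non-serious ADRs, the term defined in 9.3.1.1.

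**2. Which events this can affect.** Serious AEs are recorded whatever the causality. So are AEs that lead to discontinuation. Non-serious ISRs that do not lead to discontinuation need not be reported in any case. What remains is the middle row, restricted to non-serious AEs, other than ISRs, that do not lead to discontinuation. Such an event is in the eCRF under one threshold and out under the other.

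**3. The exclusion sentence.** Let R mean judged related and W mean led to withdrawal. I treat withdrawal and permanent discontinuation of CAB PrEP as the same, since Section 8.1 ends study participation on permanent discontinuation. The list in 9.1 records an event if R or W. The exclusion sentence, read literally, leaves it out if not-R or not-W, so it records only if R and W. For non-serious AEs other than ISRs:

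| Case | List in 9.1 and schedules | Exclusion as written | Exclusion with *and* |
|---|---|---|---|
| R, W | in | in | in |
| R, not W | in | **out** | in |
| not R, W | in | **out** | in |
| not R, not W | out | out | out |

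Two of the four cases conflict: related events without withdrawal, and unrelated events with withdrawal. With *and* in place of *or*, all four agree.

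**4. Assessor.** Section 1.2 makes the PrEP provider one of the SSPs and allows administrators, pharmacists and laboratory staff to be SSPs too. The SSP wording is therefore looser than the assignment in Section 9.3.1 and Annex 4, but it does not create a second causality assessor.

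**The case against.** The best defence of the thresholds is that they can be read together. Annex 4 defines only the phrase reasonable possibility, and Section 9.3.1.1 may deliberately add a wider limb for ADRs. That is logically possible. But Annex 4 offers no other threshold for the causality judgement, and it sets the wider limb aside by name. A provider who follows it could judge a borderline event not related, and the exclusion sentence would then keep out of the eCRF an event that Section 9.1 also requires as a non-serious ADR. The conflict stands.

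On the *or*, the defence is stronger. The list in 9.1, the paragraph after it, the opening of Section 9 and both schedules all show the intended rule, so this is probably a drafting slip and most sites would follow the list. It is still a written instruction that contradicts its own section.

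Several stronger readings are tempting but not supported.

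- *Only related non-serious AEs reach the database.* Those that lead to discontinuation are recorded whatever their relatedness.
- *Excluded events are lost.* Section 9.1 keeps them in source documents, and Section 11.7.3 requires records to be retained for 25 years. Recovering them would mean returning to site records and reassessing causality.
- *Administrators will judge causality.* Section 9.3.1 and Annex 4 give that task to the PrEP provider, and Section 3.2.1.3 requires SSPs to be qualified for their role and to act under delegation.
- *The thresholds are opposite, or ADR counts cannot be reproduced.* The thresholds differ in one band only, and nothing in the document shows how many events fall in it.

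**Conclusion.** Wrong as written. Section 9.3.1.1 and Annex 4 disagree on events whose link cannot be ruled out, and the exclusion sentence in Section 9.1 contradicts its own list in two of four cases. The consequence is limited: counts of borderline, non-serious drug-related AEs may differ between the roughly 18 sites according to which text each follows. The size cannot be computed from the protocol. This conclusion assumes that at least some sites act on the conflicting text.

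No visible primary or secondary endpoint is an AE rate and no safety hypothesis is tested, so the FIM comparisons and their sample size are unaffected. Tertiary endpoints are redacted and I draw no conclusion about them. The SSP wording is an editorial matter.

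**What to change.** 1. Reconcile Sections 9.3.1.1 and 11.4.4 to a single definition of relatedness, and state that it governs eCRF entry under Section 9.1. Which threshold to adopt is for the sponsor; what matters here is that there is one.
2. In the exclusion sentence of Section 9.1, replace *or* with *and*, so that only non-serious AEs that are both unrelated and without withdrawal stay out of the eCRF.
3. As an editorial correction, replace SSP with PrEP provider or qualified designee in that sentence and in the grading sentence of Section 9.3.1. Section 9 already provides for qualified designees.

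The cost is a wording amendment to three safety sections (9.1, 9.3.1 with 9.3.1.1, and 11.4.4) and a short note to sites. Items 2 and 3 add no collection beyond the list in Section 9.1. Item 1 settles which borderline events that list already covers. If sites have already been recording under the present text, the note should ask which definition they used, so that the safety tables can be read accordingly.

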#### **9.3.1.2. Injection Site Reactions**

Injection site reactions (ISRs) are considered drug related as they are related to the administration of CAB PrEP. ISRs may include redness, itching, pain or swelling or discomfort at the site of the reaction.

As ISRs have been well characterized throughout the clinical development program for CAB PrEP and are considered common adverse drug reactions for CAB PrEP, therefore only serious ISRs and ISRs leading to discontinuation are required to be reported to Sponsor or designee as described in [ANNEX 4](#).

#### **9.3.2. Reporting of AEs and timelines**

All SAEs will be recorded and reported to the Sponsor or designee immediately and under no circumstance should this exceed 24 hours. All AEs listed in Section [9.1.1](#) will require reporting within 3 days.

If the eCRF is unavailable at the time of notification of these events, a paper form will need to be completed and sent to the Sponsor or designee.

Prompt notification by the site to the sponsor of these events is essential so that legal obligations and ethical responsibilities towards the safety of participants and the safety of CAB PrEP are met.

#### **9.3.3. Pregnancy**

Pregnancy testing will be managed by the PrEP Provider and in accordance with CDC PrEP guidelines.

**If a pregnancy is reported, the site will record pregnancy information on the appropriate form and submit it to the Sponsor or designee within 24 hours of learning of the pregnancy. Pregnancies will also be directly reported to the Antiretroviral Pregnancy Registry (APR) by the PrEP provider. The procedure for reporting is outlined in the SRM.**

Whilst pregnancies are not part of the study **they will be reported to the Sponsor or designee within 24 hours of awareness and documented in the eCRF.** All pregnancies will be followed up until outcome (including premature terminations and complications) for both mother and child.

The PrEP Provider will be provided with necessary “pregnancy notification” and “pregnancy follow up” forms and supported by clinical monitor and/or Sponsor medical team in complying with regular pregnancy reporting procedures. Pregnancies will also be reported to the Antiretroviral Pregnancy Registry (APR) by the Sponsor. The PrEP Provider must not report to APR, to avoid duplication.

The pregnancy must be followed up to determine outcome (including premature termination) and status of mother and child(ren). Pregnancy complications and elective terminations for medical reasons must be reported as an AE or SAE. Abnormal pregnancy outcomes (e.g., spontaneous abortion, fetal death, stillbirth, congenital anomalies, ectopic pregnancy) are considered SAEs.

Any SAE occurring in association with a pregnancy brought to the site’s attention after the PSP has completed the study and considered by the PrEP Provider as possibly linked to CAB PrEP exposure, must be promptly reported to the Sponsor.

- Any post-study pregnancy-related SAE considered reasonably related to the study intervention by the PrEP Provider will be reported to the Sponsor (refer to SRM for details). While the PrEP Provider is not obligated to actively seek this information in former study participants, he or she may learn of an SAE through spontaneous reporting.
- The Sponsor’s central safety department will also forward this information to the Antiretroviral Pregnancy Registry. The international registry is jointly sponsored by manufacturers or licensees of ARV products. Additional information and a list of participating manufacturers/licensees are available from <http://apregistry.com/index.htm>.

Prior to continuation of CAB PrEP following pregnancy, the following must occur:

- PrEP Provider confirms CAB PrEP can be continued and this documentation is stored in the PSP’s source documents.
- The site agrees to monitor the outcome of the pregnancy and the status of the participant and her offspring.

#### **9.3.4. Cardiovascular and Death Events**

All deaths will be reported as SAEs. In addition, all deaths will be required to have the eCRF death forms completed by the site. These sections include questions regarding the death (including sudden cardiac death and non-cardiovascular death).

The Death eCRF is provided immediately after the occurrence or outcome of death is reported. Initial and follow-up eCRF reports regarding death must be completed within one week of when the death is reported.

For any cardiovascular events detailed in [ANNEX 4](#) and all deaths, whether or not they are considered SAEs, specific Cardiovascular (CV) and Death sections of the CRF will be required to be completed. These sections include questions regarding cardiovascular (including sudden cardiac death) and non-cardiovascular death.

The CV CRFs are presented as queries in response to reporting of certain CV MedDRA terms. The CV information should be recorded in the specific cardiovascular section of the CRF within one week of receipt of a CV Event data query prompting its completion.

### **9.3.5. Medical Device Deficiencies**

To fulfil regulatory reporting obligations worldwide, the SSP is responsible for the detection and documentation of events meeting the definitions of device deficiency that occur during the study with such devices.

The definition of a medical device deficiency can be found in [ANNEX 5](#)

NOTE: Deficiencies fulfilling the definition of an AE/SAE will also follow the processes outlined in [ANNEX 4](#) of the protocol.

#### **9.3.5.1. Time Period for Detecting Medical Device Deficiencies**

- Medical device deficiencies that result in an incident will be reported during all periods of the study in which the medical device is used.
- If the SSP learns of any device deficiency at any time after a participant has been discharged from the study, and such a device deficiency is considered reasonably related to a medical device provided for the study, the PrEP Provider will promptly notify the Sponsor.

#### **9.3.5.2. Prompt Reporting of Medical Device Deficiencies to the Sponsor**

- Device deficiencies will be reported to the sponsor within 24 hours after the SSP determines that the event meets the protocol definition of a device deficiency.
- The method of reporting of Medical device deficiencies is outlined in [ANNEX 5](#).
- The sponsor will be the contact for the receipt of device deficiency reports.

#### **9.3.5.3. Regulatory Reporting Requirements for Device Deficiencies**

- The SSP will promptly report all device deficiencies occurring with any medical device provided for use in the study in order for the sponsor to fulfil the legal responsibility to notify appropriate regulatory authorities and other entities about certain safety information relating to medical devices being used in clinical studies.
- The SSP, or responsible person according to local requirements (e.g., the head of the medical institution), will comply with the applicable local regulatory requirements relating to the reporting of device deficiencies to the IRB/IEC.

## 11. ANNEX

### 11.1. ANNEX 1: Schedule of Activities – Direct to injection

Procedure 	Screening/ Enrollment Up to 90 days 	Treatment Period  Month(M)/Dose(D)												E.D. 	Notes
		M1	M2	M3	M4	M5	M6	M7	M8	M9	M10	M11	M12		
		D1  visit	D2 visit		D3 visit		D4 visit		D5 visit		D6 visit		D7 visit		

1. The timing and number of planned study assessments, specifically interviews with SSPs and PSPs, may be altered during the study based on newly available data. Brief interviews may be held at other times based on learnings during implementation.
 
2. Benefits verification should be performed at the start of the screening period, which may be extended up to 90 days to allow for this confirmation. All other screening/eligibility procedures (excluding informed consent) should only be performed after receiving this benefits confirmation. Additionally, in line with the USPI, all patient participants require proof of a negative HIV test, dated within the 7 days prior to PrEP initiation, regardless of any prior negative test results. During screening/enrollment, the following will be completed for PSPs: 1) Informed consent form (ICF), 2) Benefits verification, as required, 3) Confirm Inclusion and Exclusion criteria, 4) Demography 5) Medical History, including history of HCV infection, and current medical conditions 6) required labs per clinical local standard of care. Screening/enrollment can occur on the same date as the first APRETUDE injection as long as a negative HIV test is documented within 7 days prior to initiation of APRETUDE. Refer to Section 3.3.1 for details on re-screening for PSPs who fail screening.
 
3. Dose 1(D1) is defined as the date of first APRETUDE injection. The following sequence of events must be followed for participants at the D1 visit: 1) complete questionnaires and assessments prior to or at the visit, and 2) Receive first intramuscular (IM) injections at the visit.
 
4. The treatment period is based on 12 calendar months. The last APRETUDE injection is to occur at the last study visit.
 
5. E.D. = early discontinuation/ withdrawal: This visit should only be conducted if the participant discontinues from the study prior to completing the Study at Month 12, and the discontinuation/withdrawal reason should be recorded. For SSPs, this visit will only occur if the SSP withdraws and remains in the role for which they were enrolled and no replacement is possible.
															

Procedure 	Screening/ Enrollment Up to 90 days 	Treatment Period  Month(M)/Dose(D)												E.D. 	Notes
		M1	M2	M3	M4	M5	M6	M7	M8	M9	M10	M11	M12		
		D1  visit	D2 visit		D3 visit		D4 visit		D5 visit		D6 visit		D7 visit		
Clinical and Other Assessments															
Informed consent	X														Written informed consent must be obtained from each potentially eligible participant by site personnel prior to the initiation of any M1 procedures as outlined in this protocol.
Inclusion and exclusion criteria	X														Inclusion/exclusion criteria will be assessed during screening.
Benefits verification, as needed	X														
Demography	X														
Medical History	X														
Current Medical Conditions	X														

Procedure 	Screening/ Enrollment Up to 90 days 	Treatment Period  Month(M)/Dose(D)												E.D. 	Notes
		M1	M2	M3	M4	M5	M6	M7	M8	M9	M10	M11	M12		
		D1  visit	D2 visit		D3 visit		D4 visit		D5 visit		D6 visit		D7 visit		
Laboratory assessments	X – needed at BL, M6 and end of study, can be just HIV test and STI testing, but shouldn't be completely non-prescriptive.	
Lab assessments, including HIV testing and STI clinical diagnoses (defined for this study as syphilis (any stage), gonorrhea, chlamydia, or trichomonas) at Screening and during PrEP should be performed using local laboratories and should be in accordance with the CDC PrEP clinical management guidelines and the USPI or per clinical local standard of care. All lab reports must be stored in the participants source documentation at the clinical sites with only the protocol-specified test results to be reported in the eCRF*.
 
For PSPs with incident HIV-1 infections, all available HIV-1 test results (HIV Test Result (positive, Negative and Indeterminate), HIV Test Type (HIV-1 Antibody/Antigen test and HIV-1 RNA)) conducted by the site as standard of care and, if applicable and available, the start date of ART and ART regimen (by category) used will be reported in the eCRF.
												x	*All performed HIV test results (regardless of result, including positive, negative, or indeterminate) and HIV test type will be reported in the eCRF.

Study Treatment: Participants who are started on oral CAB PrEP as optional oral lead in will receive their first dose of oral CAB on M1. Participants who are started on APRETUDE injections (direct to injection) will receive their first dose of APRETUDE injection on M1.
 
All injections will be administered according to the APRETUDE USPI.
															
Cabotegravir LA PrEP IM Initiation injection		X													

Procedure 	Screening/ Enrollment Up to 90 days 	Treatment Period  Month(M)/Dose(D)												E.D. 	Notes
		M1	M2	M3	M4	M5	M6	M7	M8	M9	M10	M11	M12		
		D1  visit	D2 visit		D3 visit		D4 visit		D5 visit		D6 visit		D7 visit		
Cabotegravir LA PrEP IM Maintenance injections			X		X		X		X		X		X		IM dosing is expected to occur on the same date of the month as determined by Dose 1 - Treatment Target Date. Dosing window is (+ or -) a 7-day window, as per the USPI.
Concomitant medication review	X													X	Record in CRF if; contraindicated medications, concomitant medications with a potential for a drug-drug interaction (DDI) per the CAB tablet for PrEP or APRETUDE USPI;

Procedure 	Screening/ Enrollment Up to 90 days 	Treatment Period  Month(M)/Dose(D)												E.D. 	Notes
		M1	M2	M3	M4	M5	M6	M7	M8	M9	M10	M11	M12		
		D1  visit	D2 visit		D3 visit		D4 visit		D5 visit		D6 visit		D7 visit		
Adverse Event (AE) Review		X												X	Only drug related AEs and AEs leading to CAB Prep discontinuation will be collected in the eCRF.
Serious AEs (SAEs)	X													X	All SAEs regardless of relatedness will be collected in the eCRF.
Pregnancy status	X													X	Ask person of childbearing potential at each visit if they are pregnant and ask for the date of their LMP.
Questionnaires and Interviews: Questionnaires and Interviews should be completed before receiving APRETUDE IM injections															

Procedure 	Screening/ Enrollment Up to 90 days 	Treatment Period  Month(M)/Dose(D)												E.D. 	Notes	
		M1	M2	M3	M4	M5	M6	M7	M8	M9	M10	M11	M12			
		D1  visit	D2 visit		D3 visit		D4 visit		D5 visit		D6 visit		D7 visit			
Patient Study Participants																
PSP baseline questionnaires should be completed within two weeks prior to or on their D1 visit and before receiving the 1 st APRETUDE injection.																
Participants interviews should be completed within two weeks prior to or two weeks following their D1 visit and within two weeks prior to or two weeks following the target dates for their D4 and D7 visits. Approximately 3 participants per site will be interviewed; sites with larger volume of participants might have more interviews. Participants will be purposely sampled for interviews based on demographic characteristics, such as race/ethnicity, prior PrEP use.																
All additional study visits, including those where questionnaires and/or interviews are administered at M6 and M12, will be anchored off of each participants M1 visit, so it reflects months in study, regardless of what dose they are on and regardless of whether they have missed any injections and received oral PrEP.																
PSP Questionnaires		X					X							X	X	To be completed prior to injection.
Participant Interviews		X					X							X	X	Interviews will be completed on a subset of PSPs (see Section 4.1.3.1). Window within 2 weeks before or 2 weeks following study visit.

Procedure 	Screening/ Enrollment Up to 90 days 	Treatment Period  Month(M)/Dose(D)												E.D. 	Notes
		M1	M2	M3	M4	M5	M6	M7	M8	M9	M10	M11	M12		
		D1  visit	D2 visit		D3 visit		D4 visit		D5 visit		D6 visit		D7 visit		

